Acute vascular leak syndrome	Acute vascular leak syndrome	—	Symptomatic, fluid support not indicated	Respiratory compromise or fluids indicated	Life-threatening; pressor support or ventilatory support indicated	Death
Peripheral arterial ischemia	Peripheral arterial ischemia	—	Brief (<24 hrs) episode of ischemia managed non-surgically and without permanent deficit	Recurring or prolonged (≥24 hrs) and/or invasive intervention indicated	Life-threatening, disabling and/or associated with end organ damage (e.g., limb loss)	Death
Phlebitis (including superficial thrombosis)	Phlebitis	—	Present	—	—	—
ALSO CONSIDER: Injection site reaction/extravasation changes.						
Portal vein flow	Portal flow	—	Decreased portal vein flow	Reversal/retrograde portal vein flow	—	—
Thrombosis/embolism (vascular access-related)	Thrombosis/embolism (vascular access)	—	Deep vein thrombosis or cardiac thrombosis; intervention (e.g., anticoagulation, lysis, filter, invasive procedure) not indicated	Deep vein thrombosis or cardiac thrombosis; intervention (e.g., anticoagulation, lysis, filter, invasive procedure) indicated	Embolitic event including pulmonary embolism or life-threatening thrombus	Death
Thrombosis/thrombus/embolism	Thrombosis/thrombus/embolism	—	Deep vein thrombosis or cardiac thrombosis; intervention (e.g., anticoagulation, lysis, filter, invasive procedure) not indicated	Deep vein thrombosis or cardiac thrombosis; intervention (e.g., anticoagulation, lysis, filter, invasive procedure) indicated	Embolitic event including pulmonary embolism or life-threatening thrombus	Death
Vessel injury-artery – Select : – Aorta – Carotid – Extremity-lower – Extremity-upper – Other NOS – Visceral	Artery injury – Select	Asymptomatic diagnostic finding; intervention not indicated	Symptomatic (e.g., claudication); not interfering with ADL; repair or revision not indicated	Symptomatic interfering with ADL; repair or revision indicated	Life-threatening; disabling; evidence of end organ damage (e.g., stroke, MI, organ or limb loss)	Death
NAVIGATION NOTE: Vessel injury to an artery intra-operatively is graded as Intra-operative injury – Select Organ or Structure in the SURGERY/INTRA-OPERATIVE INJURY CATEGORY.						

VASCULAR

		Grade				
Adverse Event	Short Name	1	2	3	4	5

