10.6 Efficacy, Safety, and Pharmacodynamic Evaluations

10.6.1 Primary Analyses

10.6.1.1 Safety Analysis

In general, safety assessments will be based on all assessments post-baseline. The assessment of safety will be based primarily on the frequency of AEs, and on the frequency of clinically notable abnormal vital sign and laboratory values. Changes from baseline will be calculated by subtracting the baseline value from the post-baseline value.

All enrolled patients who had an IDDD surgical procedure and/or received administration of HGT-1410 will be included in the safety analysis.

Adverse events will be recorded throughout the study and at early termination. Adverse events and medical conditions will be coded using the Medical Dictionary for Regulatory Activities (MedDRA).

Adverse events will be summarized by presenting, for each dose group, the number and percentage of patients having any AE, having an AE in system organ class, and having each individual AE. In addition, those events which resulted in death or were otherwise classified as serious will be presented in a separate listing. The incidence of treatment-emergent adverse events, defined as all AEs from the time of the surgery for IDDD implantation to the last follow up contact, ie, 30 days after the last HGT-1410 administration, (new or worsened from baseline) will be summarized by system organ class, severity, type of adverse event and relationship to trial medication/procedure.

Treatment-emergent AEs deemed related to HGT-1410 administration will be summarized separately.

IDDD and procedure-related AEs will be summarized within system organ class by preferred term. IDDD and procedure-related AEs will be tabulated by severity (mild, moderate, severe) and degree of relatedness. Separate tabulations will be provided for adverse events related to the IDDD, device surgical procedure (including post-implant infections) and IT administration process. These summaries will be presented by device and overall, as appropriate.

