Descriptive summaries of clinical laboratory evaluations (hematology, serum chemistry, urinalysis and CSF) results will be presented in summary tables by evaluation visit. Changes from baseline will be summarized for each post-baseline visit. Each laboratory result will be categorized as a patient having had (1) an Abnormal and Clinically Significant (CS) value at any time, (2) no CS values at any time but had at least one Abnormal and not CS (NCS) value, and (3) no CS or NCS values at any time; the number and percentage in each category will be presented. For any patient who experiences a CS laboratory result at any time that was not CS at

baseline (or the most recent non-missing value prior to the start of the treatment), their entire profile for that particular laboratory parameter will be presented as a listing.

The observed values and changes from baseline for vital sign data will be summarized for each dose group. Shift tables may be presented, utilizing reference ranges. Patients with notably abnormal values will be identified and listed separately along with their values.

The observed values and changes from baseline for ECG data will be summarized for each dose group. Patients with any clinically significant findings and/or conduction abnormalities will be listed separately along with their values.

Anti-rhHNS antibody formation will be monitored throughout the study. Results will be presented in summary tables by number and percentage of positive and negative specimens by evaluation visit, and number and percentage of positive and negative specimens overall. The effect of antibodies on other safety parameters will be assessed by presenting summary tables by antibody status.

For those patients who fail to complete the study, the reason for discontinuation will be listed by patient and dose group.

Listings of all study safety data will be presented.

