Edema: trunk/genital	Edema: trunk/genital	Swelling or obscuration of anatomic architecture on close inspection; pitting edema	Readily apparent obscuration of anatomic architecture; obliteration of skin folds; readily apparent deviation from normal anatomic contour	Lymphorrhea; interfering with ADL; gross deviation from normal anatomic contour	Progression to malignancy (i.e., lymphangiosarcoma); disabling	Death
Edema: viscera	Edema: viscera	Asymptomatic; clinical or radiographic findings only	Symptomatic; medical intervention indicated	Symptomatic and unable to aliment adequately orally; interventional radiology or operative intervention indicated	Life-threatening consequences	Death

LYMPHATICS

		Grade				
Adverse Event	Short Name	1	2	3	4	5
Lymphedema-related fibrosis	Lymphedema-related fibrosis	Minimal to moderate redundant soft tissue, unresponsive to elevation or compression, with moderately firm texture or spongy feel	Marked increase in density and firmness, with or without tethering	Very marked density and firmness with tethering affecting $\geq 40\%$ of the edematous area	—	—
Lymphocele	Lymphocele	Asymptomatic, clinical or radiographic findings only	Symptomatic; medical intervention indicated	Symptomatic and interventional radiology or operative intervention indicated	—	—
Phlebolympatic cording	Phlebolympatic cording	Asymptomatic, clinical findings only	Symptomatic; medical intervention indicated	Symptomatic and leading to contracture or reduced range of motion	—	—
Lymphatics – Other (Specify, __)	Lymphatics – Other (Specify)	Mild	Moderate	Severe	Life-threatening; disabling	Death

METABOLIC/LABORATORY

Page 1 of 3

Adverse Event	Short Name	Grade				
		1	2	3	4	5
Acidosis (metabolic or respiratory)	Acidosis	pH <normal, but ≥ 7.3	—	pH <7.3	pH <7.3 with life-threatening consequences	Death
Albumin, serum-low (hypoalbuminemia)	Hypoalbuminemia	<LLN – 3 g/dL <LLN – 30 g/L	<3 – 2 g/dL <30 – 20 g/L	<2 g/dL <20 g/L	—	Death
Alkaline phosphatase	Alkaline phosphatase	>ULN – 2.5 x ULN	>2.5 – 5.0 x ULN	>5.0 – 20.0 x ULN	>20.0 x ULN	—
Alkalosis (metabolic or respiratory)	Alkalosis	pH >normal, but ≤ 7.5	—	pH >7.5	pH >7.5 with life-threatening consequences	Death
ALT, SGPT (serum glutamic pyruvic transaminase)	ALT	>ULN – 2.5 x ULN	>2.5 – 5.0 x ULN	>5.0 – 20.0 x ULN	>20.0 x ULN	—
Amylase	Amylase	>ULN – 1.5 x ULN	>1.5 – 2.0 x ULN	>2.0 – 5.0 x ULN	>5.0 x ULN	—

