3 STUDY ENDPOINTS

3.1 Primary Endpoint

The primary endpoints of this study are related to the long-term safety of intrathecal HGT-1410 administration. The safety endpoints are:

[figure not shown]
- adverse events (type and severity)
- changes in clinical laboratory testing (serum chemistry including liver function tests, hematology, and urinalysis)
- electrocardiograms (ECG)
- CSF chemistries (including cell counts and inflammatory markers)
- anti-rhHNS antibodies (in CSF and serum).

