7.22.3 Classification of Adverse Events and Serious Adverse Events

The National Cancer Institute Common Terminology Criteria for Adverse Events (NCI CTCAE) version 3.0 grading scale should be referenced when assessing the severity of an AE (see [Appendix 6](#)). If an AE is not described in the NCI CTC, the severity should be recorded based on the scale provided in Table 7-3. The severity of all AEs/SAEs should be recorded on the appropriate eCRF page. Adverse events are graded as Grade 1, 2, 3, 4, or 5 corresponding, respectively, to a severity of mild, moderate, severe, life-threatening, or death.

Table 7-3 Adverse Event Severity

Severity	Definition
Grade 1 (Mild)	No limitation of usual activities.
Grade 2 (Moderate)	Some limitation of usual activities.
Grade 3 (Severe)	Inability to carry out usual activities.
Grade 4 (Life-threatening)	Immediate risk of death.
Grade 5 (Death related to an AE)	Death

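### The only stated table that counts patients by laboratory abnormality (Section 10.6.1.1) rests on a clinical-significance flag with no numeric limit, and no stated output counts patients by worst grade against their own baseline

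*Protocol*

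**What the plan says.** Section 3.1 names among the primary safety endpoints "changes in clinical laboratory testing (serum chemistry including liver function tests, hematology, and urinalysis"). Section 10.6.1.1 says that safety will be judged mainly on the frequency of adverse events and "on the frequency of clinically notable abnormal vital sign and laboratory values".

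For laboratory data, the same section gives a three-way split, with numbers and percentages to be shown: "Each laboratory result will be categorized as a patient having had (1) an Abnormal and Clinically Significant (CS) value at any time"; then "no CS values at any time but had at least one Abnormal and not CS (NCS) value"; then neither. It adds a profile listing: "For any patient who experiences a CS laboratory result at any time that was not CS at" baseline, the whole series for that test is printed. Neither CS nor clinically notable has a numeric limit in the text shown.

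Numeric limits do exist elsewhere. Section 7.22.3 says that the CTCAE "version 3.0 grading scale should be referenced when assessing the severity of an AE", and Appendix 6 reproduces that scale, including ">5.0 – 20.0 x ULN" as Grade 3 for ALT. Section 6.5 confirms that there is no blinding.

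The Section 10 wording is that of Amendment 6. The text of Amendment 7 stops at the heading of Section 8.1.

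**The concern.** The middle category has no upper bound. Whether a patient lands in it or in the first category depends on a flag that has no stated criterion and is set in a study where dose and time on drug are known. Either way, the size of the abnormality is not kept.

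The profile trigger inherits the same weakness and adds another. It needs a CS value in a patient who was not CS at baseline. A child with a large rise that is not flagged gets no profile, and neither does a child who was already CS at baseline and then worsens.

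Liver function tests are named in the primary endpoint, and the study has at most 12 patients. A reader of the report will want to know how many children reached which grade, starting from where. The stated outputs do not answer that directly.

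**Working it through.** There is no sample-size, power or event figure to reproduce: Section 10.1 is descriptive and Section 10.2 makes no calculation. The check is to put the same hypothetical ALT values through both rules.

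Inputs:
- CTCAE v3.0 limits for ALT (Appendix 6): Grade 1 above ULN to 2.5 x ULN; Grade 2 above 2.5 to 5.0; Grade 3 above 5.0 to 20.0; Grade 4 above 20.0. AST, GGT and alkaline phosphatase have the same limits.
- Section 10.6.1.1: category 1 if any value is CS; category 2 if abnormal but never CS; category 3 if neither.

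| Worst ALT (x ULN) | CTCAE grade | Category if not flagged CS | Category if flagged CS |
|---|---|---|---|
| 0.9 | none | 3 | 3 |
| 1.01 | 1 | 2 | 1 |
| 2.6 | 2 | 2 | 1 |
| 5.1 | 3 | 2 | 1 |
| 20.1 | 4 | 2 | 1 |

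Within category 2, 5.1 x ULN sits beside 1.01 x ULN (5.1 / 1.01 = 5.05-fold) and 20.1 x ULN sits beside it too (20.1 / 1.01 = 19.9-fold). Category 1 mixes grades in the same way. The split therefore carries the flag but not the grade.

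The profile rule, applied to two children:
- Normal at baseline, worst value 8 x ULN (Grade 3), not flagged: no CS value, so no profile.
- Grade 2 and CS at baseline, Grade 4 and CS later: not newly CS, so no profile.

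Weight of one patient: with the maximum of 12, one child moved between categories shifts a percentage by 1/12 = 8.3 points. If the three dose groups were equal (assumed: 12/3 = 4 each), the shift within a group is 1/4 = 25 points.

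The other stated outputs, set against the question of how many children worsened and to what grade:
- By-visit summaries (Sections 10.1 and 10.6.1.1) include the maximum value and the maximum change. In a small group the maximum change is one child's own rise, so an extreme child is visible. It is not stated as a multiple of an age-appropriate ULN, and it does not show whether maxima at different visits belong to one child or several.
- Listings of all safety data hold every value but count nothing.
- Adverse event tables by severity use CTCAE grades, but only for values recorded as events. Section 7.22.1.1 names abnormal laboratory values as events, then says that events may also include values significantly out of range, again without a limit.

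**The case against.** The strongest reply is that this belongs to the SAP. Section 10.6.4 defers final presentations to it, it is not shown, and grade shift tables are often specified there. That would settle the matter if the protocol were silent. It is not: Section 10.6.1.1 fixes the three categories and the profile trigger, and a SAP that follows the protocol inherits both. What stands is that nothing bars the SAP from adding a grade table or defining CS.

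A second reply is that magnitude is not lost, since listings, by-visit maxima and graded adverse events remain. This stands in large part. A reader might infer that a Grade 3 or Grade 4 ALT could go unreported; the documents do not support that.

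Third, CTCAE is adopted for adverse event severity, not as a laboratory-table scale. This also stands: the Appendix 6 limit is not wrong, and there is no contradiction between it and Section 10.6.1.1.

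Fourth, a reader might infer that investigators will under-flag because they know the dose. Section 10.6.1.1 does not say who sets the flag, and the study has no control arm and tests no hypothesis, so bias is possible but not shown.

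**Conclusion.** The point holds in a limited form. The only stated table that counts patients by laboratory abnormality depends on an undefined flag and can place Grades 1 to 4 together, and the profile trigger misses unflagged rises and worsening from a CS baseline. No stated output counts patients by worst abnormality against their own baseline, although laboratory change is a primary safety endpoint.

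Its size cannot be given as a rate. A reader might infer that the CS percentage understates the share of children with Grade 3 values by some factor, but the documents give neither the number of such children nor how often values are flagged, and the CS table does not claim to estimate that share. The firm figures are the four grades that one category can span and the 8.3 percentage points that one child of 12 represents.

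This is a weakness in summarising data, not a loss of data, and it is worth correcting because correction is cheap. It rests on the Amendment 6 wording being carried into Amendment 7, which cannot be checked here.

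**What to change.** In Section 10.6.1.1, or in the SAP under it:
- Keep the CS / not CS table and state the criterion for CS and for clinically notable.
- For each test with CTCAE v3.0 numeric limits, add a shift table of baseline grade against worst post-baseline grade, computed from the central-laboratory value (Section 7.7) with age-appropriate reference limits.
- Print the patient profile for any post-baseline increase to Grade 2 or higher, or for a CS flag.
- Leave the CSF chemistries and cell counts, which Section 7.7.6.1 assigns to local laboratories, on the CS / not CS flag.
- Confirm that the change is made in the Section 10 that is in force under Amendment 7.

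The cost is one derived variable, its programming and a few more profiles. No new samples or visits are needed. It assumes that age-appropriate reference limits are available for each central-laboratory test; Section 11.7.1 already requires reference-range documentation.

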Appendix 6	The National Cancer Institute Common Terminology Criteria version 3.0.....	93

SYNOPSIS

Sponsor:

Shire Human Genetic Therapies, Inc.
[name]
[name]
[REDACTED]

Name of Finished Product:

Recombinant human heparan N-sulfatase (rhHNS, HGT-1410)

Name of Active Ingredient:

rhHNS, HGT-1410

Name of Inactive Ingredient:

N/A

Names of Devices:

SOPH-A-PORT[®] Mini S, Implantable Access Port, Spinal, Mini Unattached, with
Guidewire (SOPH-A-PORT Mini S)

and

PORT-A-CATH[®] II Low Profile[™] Intrathecal Implantable Access System
(PORT-A-CATH)

Study Title:

An Open-Label Extension of Study HGT-SAN-055 Evaluating Long-Term Safety and
Clinical Outcomes of Intrathecal Administration of rhHNS in Patients with Sanfilippo
Syndrome Type A (MPS IIIA)

Study Number:

HGT-SAN-067

Study Phase: I/II

Device, Intended Use

The SOPH-A-PORT Mini S is a system intended for implantation by physicians. The
SOPH-A-PORT Mini S, once implanted, allows healthcare personnel to administer
HGT-1410 indicated for intrathecal delivery intermittently over a long period of time.

Prior to approval of Amendment 4, patients were implanted with a PORT-A-CATH
(Smith's device). After approval of Amendment 4 all PORT-A-CATH IDDDs requiring
revision or replacement will be replaced with a SOPH-A-PORT at a time judged
appropriate by the investigator.

Study Objectives:

Primary Objective:

The primary objective of this study is:

- To collect long-term safety and tolerability data in patients with Sanfilippo Syndrome Type A (MPS IIIA) who received HGT-1410 via a surgically implanted intrathecal drug delivery device (IDDD) in study HGT-SAN-055 and elected to continue therapy in study HGT-SAN-067.
-

Secondary Objectives:

The secondary objectives of this study are:

- To collect as measures of drug efficacy, over an extended treatment period (as change from baseline), the following: clinical, neurological, cognitive, behavioral, functional, and quality of life (QoL) assessments, together with potential imaging and biochemical biomarkers.

Study Endpoints:

Primary Endpoints:

The primary endpoints of this study are related to the long-term safety of intrathecal HGT-1410 administration. The safety endpoints are:

- adverse events (type and severity)
- changes in clinical laboratory testing (serum chemistry including liver function tests, hematology, and urinalysis)
- electrocardiograms (ECG)
- cerebrospinal fluid (CSF) chemistries (including cell counts and inflammatory markers)
- anti-rhHNS antibodies (in CSF and serum).

Secondary Endpoints:

The secondary endpoints of this study are to collect over an extended treatment period (as change from baseline) clinical and potential surrogate biomarker efficacy data:

- Standardized neurocognitive and behavioral assessments, Sanfilippo-specific behavioral rating scales, gross and fine motor assessments, functional adaptive rating scales, quality of life questionnaires, and Children's Sleep Habits Rating Scale.
- Concentration of safety and potential surrogate efficacy biomarkers in CSF, urine, and serum.
- Concentration of heparan sulfate and heparan sulfate derivatives in CSF and glycosaminoglycans (GAG), including heparan sulfate and heparan sulfate derivatives, in urine.
- Brain magnetic resonance imaging (MRI) and auditory brainstem response (ABR), Brainstem Auditory Evoked Potentials).

Study Design:

This study, HGT-SAN-067, is an open-label, long term, multicenter, extension of Study HGT-SAN-055. The study is designed to evaluate the long-term safety, clinical activity, and biomarker outcomes of intrathecal (IT) administration of 3 dose levels (10 mg, 45 mg, and 90 mg once per month [Q4W]) of HGT-1410 via an IDDD in patients with MPS IIIA who successfully complete the Phase I/II study HGT-SAN-055 (including end of study [EOS] assessments) and elect to continue to receive HGT-1410 treatment. Initially, patients will continue in the same treatment group they were assigned to in the HGT-SAN-055 study. Following approval of protocol Amendment 4, patients in the 10 mg group had their dose increased to 45 mg per month.

For nomenclature of chronology purposes, the Baseline Visit for this extension study will be considered to be the first day the patient received his/her IT dose of HGT-1410 in

Study HGT-SAN-055. The HGT-SAN-055 EOS assessment information will provide the screening/start of study information for patients who continue into the HGT-SAN-067 extension study. Note: HGT-SAN-055 EOS data must be recorded in the context of the HGT-SAN-055 trial, and a copy of those data can be used for HGT-SAN-067 screening. Once eligibility is confirmed, informed consent must be obtained prior to performing any study-related procedures that are specific to HGT-SAN-067.

Informed consent will be provided by the patient's parent(s)/legally authorized representative(s) prior to the start of the extension study procedures. Informed consent may be obtained anytime from week 20 in HGT-SAN-055. This would allow a patient to have a nonfunctional IDDD replaced or revised prior to the first HGT-1410 dose in HGT-SAN-067.

Enrolled patients will check in to the study center 1 day before each of the scheduled HGT-1410 dosing days for safety assessments (designated Day 1). If no safety concerns exist, the patient will subsequently receive IT administration of HGT-1410 on Day 2 (± 2 days). However, if feasible and there are no safety concerns in the opinion of the investigator, the Day 1 and Day 2 assessments may be combined and performed on Day 2; if this is done the results will be recorded as Day 2. Patients will remain in the study center for at least 4 hours following dosing with HGT-1410 and will be discharged from the unit when deemed clinically stable by the investigator.

All patients will have received a series of standardized neurodevelopment assessments in the HGT-SAN-055 study. These assessments will have occurred at Baseline and either prior to or at the 6-month time point. Patients will continue in HGT-SAN-067 with whichever age specific assessment they began with in HGT-SAN-055. If, however, a patient's capability improves and they become capable of completing assessments at a higher level, such additional assessments may be added. Any additional assessments would be performed after the original assessments (those previously used in study HGT-SAN-055) have been carried out. An MRI of the head will be performed at Months 12, 24, 36, 54, 60, 72, 84, 96, and 102 and ABR testing will be performed at Months 12, 24, and 36 (note that assessment time point nomenclature includes the 6 months in the HGT-SAN-055 study). Note: X-rays may be performed to investigate device malfunction, and to verify correct catheter and port placement following surgical implantation or revision. In addition, fluoroscopy should be employed intraoperatively to guide catheter placement. Thus, patients may undergo 3 X-ray examinations in association with each episode of IDDD malfunction and subsequent IDDD revision or replacement. Since the number of IDDD revisions/replacements is limited to 2 in any 6-month period (including the time in the HGT-SAN-055 study), the number of protocol-associated X-ray evaluations is limited to 6 exposures in any 6-month period (including time in the HGT-SAN-055). Patients will also have X-ray examinations of the device performed at the EOS visit if the patient is to continue to receive intrathecal HGT-1410 beyond the end of the study.

Patients will be evaluated for safety throughout the study. Adverse events that occur in HGT-SAN-055 and that are ongoing at enrollment in HGT-SAN-067 will be captured in the case report forms (CRFs) for study HGT-SAN-067. Specific safety stopping criteria

will be applied and will be based on the types and severity of adverse events (AEs) reported while on-study. These data will be reviewed to inform the decision to discontinue a patient, a dose group, or the study as a whole.

All patients will have an EOS visit 30 (± 7) days following their last administration of HGT-1410 (ie, Month 102). The EOS procedures will include standard clinical laboratory tests (serum chemistry, hematology, and urinalysis) in CSF and blood, protocol specific laboratory testing (eg, anti-rhHNS antibody testing), neurodevelopmental testing, child health questionnaires, and MRI.

Use of concomitant medications, therapies, and procedures will be recorded and AEs will be monitored.

All patients will be contacted by telephone or will have a visit for a Final Safety Follow-up, to be conducted at 30 (± 7) days after the EOS visit (ie, Month 103) to collect updated information on AEs and concomitant medications, therapies, and procedures.

It is anticipated that the IDDD will be used to obtain CSF samples and to deliver administrations of HGT-1410. However, if a patient's IDDD appears nonfunctional or if its use is precluded on a scheduled day of dosing, site personnel will refer to the operations manual (for PORT-A-CATH) or the IDDD Manual (for SOPH-A-PORT), which describes the investigation and management of IDDD-related issues. This will include possible partial revision or complete replacement of the IDDD. As noted above, a maximum of 2 partial revisions and/or complete replacements can occur in any 6 month period. If revision or replacement of the IDDD cannot be scheduled in time to avoid a delay of the next scheduled dose of HGT-1410, or if the patient experiences more than 2 IDDD malfunctions in a 6 month period (including participation in study HGT-SAN-055), HGT-1410 will be administered via lumbar puncture (LP).

If there are medical contra-indications to the re-implantation of a new device, or if the patient so desires, repeat monthly lumbar punctures may be considered as an alternative way of delivering the study drug and obtaining CSF samples under limited circumstances. If no safety risks are identified by the investigator, up to 12 consecutive lumbar punctures may be performed across the studies HGT-SAN-055 and HGT-SAN-067. Once a patient has reached the maximum of 12 consecutive lumbar punctures, a new IDDD may be re-implanted for subsequent dosing, unless, in the opinion of the investigator and medical monitor, assessment of risk/benefit favors continued dosing via lumbar puncture.

Continued treatment via lumbar puncture beyond the stipulated 12 consecutive monthly doses can be considered only in individual cases where this treatment is very well tolerated and the investigator has not identified any safety concerns associated with repeat lumbar puncture and repeat sedation/anesthesia.

If there is no significant safety risk in the opinion of the investigator, a non-functional IDDD may be left in situ for up to 3 months.

In light of the higher than expected complications experienced with the PORT-A-CATH IDDD, the SOPH-A-PORT Mini S device will be introduced for those patients requiring

replacement or revision. This new device has design features anticipated to reduce complications encountered with the PORT-A-CATH IDDD device. Specific device assessments are included in the protocol to collect information with respect to information specific to SOPH-A-PORT Mini S device safety and function.

Patients who discontinue or are withdrawn before receiving 3 monthly IT injections will not have to undergo the EOS evaluations but will have their IDDD removed.

Patients will have the IDDD removed when they discontinue from the study, unless the patient is continuing to receive treatment through another mechanism (eg, extension study, expanded access, commercially available).

An overview of the study appears in the Schedule of Events.

Study Population:

A maximum of 12 patients are planned for this study. To be eligible for participation patients will have completed all study requirements in Study HGT-SAN-055, including the EOS visit, and will have elected to continue treatment with HGT-1410.

Test Product; Dose; and Mode of Administration: Recombinant human heparan N-sulfatase (rhHNS, HGT-1410) will be administered via an IDDD according to the same dose to which the patient was assigned in HGT-SAN-055 (ie, 10 mg, 45 mg, or 90 mg monthly). Patients assigned to the 10 mg monthly dose had their dose increased to 45 mg once per month (Q4W) at the first administration of HGT-1410.

Reference Therapy; Dose; and Mode of Administration:

N/A

Diagnosis and Main Criteria for Inclusion

Inclusion Criteria:

Each patient must meet the following criteria to be enrolled in this study.

1. The patient must have completed Study HGT-SAN-055 and, in the opinion of the investigator, have no safety or medical issues that contraindicate participation.
 2. The patient, patient's parent(s) or legally authorized representative(s) has voluntarily signed an Institutional Review Board/Independent Ethics Committee-approved informed consent (and assent, if applicable) form after all relevant aspects of the study have been explained and discussed with them. Informed consent/assent must be obtained prior to any study specific procedures.
 3. The patient received at least 5 of the 6 planned infusions of HGT-1410 in the HGT-SAN-055 study.
 4. The patient must be medically stable, in the opinion of the investigator, to accommodate the protocol requirements, including travel, assessments, and IDDD surgery (if necessary for replacement purposes), without placing an undue burden on the patient/patient's family.
-

Exclusion Criteria:

Patients will be excluded from the study if there is evidence of any of the following:

1. The patient has experienced an adverse reaction to study drug in Study HGT-SAN-055 that contraindicates further treatment with HGT-1410.
2. The patient has a known hypersensitivity to the active ingredient or any excipients in HGT-1410 drug product.
3. The patient has non-MPS IIIA related central nervous system (CNS) impairment or behavioral disturbances that would confound the scientific integrity or interpretation of study assessments, as determined by the investigator.
4. The patient has MPS IIIA behavioral-related issues, as determined by the investigator, which would preclude performance of study neurocognitive and developmental testing procedures.
5. The patient is pregnant, breast feeding, or is a patient of childbearing potential who will not or cannot comply with the use of an acceptable method of birth control, such as condoms, barrier method, oral contraception, etc.
6. The patient has any known or suspected hypersensitivity to anesthesia or is thought to have an unacceptably high risk for anesthesia due to airway compromise or other conditions.
7. The patient has a history of a poorly controlled seizure disorder.
8. The patient is currently receiving psychotropic or other medications, which in the investigator's opinion, would be likely to substantially confound test results and the dose and regimen of which cannot be kept constant throughout the study.
9. The patient cannot sustain absence from aspirin, non-steroidal medications, or medications that affect blood clotting within 1 week prior to a relevant study-related procedure (eg, device re-implantation if applicable), or has ingested such medications within 1 week before any procedures in which any change in clotting activity would be deleterious.
10. The patient has received treatment with any investigational drug (other than HGT-1410) intended as a treatment for MPS IIIA within the 30 days prior to, during the study, or is currently enrolled in another study that involves an investigational drug or device (screening through safety follow-up contact).
11. The patient has received a hematopoietic stem cell or bone marrow transplant.

For patients to be implanted with the SOPH-A-PORT Mini S IDDD the following conditions are contraindicated, as described in the Instructions for Use:

1. The patient has had, or may have, an allergic reaction to the materials of construction of the SOPH-A-PORT Mini S device
 2. The patient's body size is too small to support the size of the SOPH-A-PORT Mini S Access Port, as judged by the investigator
 3. The patient has a known or suspected local or general infection
 4. The patient is at risk of abnormal bleeding due to a medical condition or therapy
 5. The patient has one or more spinal abnormalities that could complicate safe implantation or fixation
 6. The patient has a functioning CSF shunt device
-

7. The patient has shown an intolerance to an implanted device

Duration of Treatment:

The study duration allows patients who completed Study HGT-SAN-055 and elected to continue treatment with HGT-1410 in Study HGT-SAN-067 to receive treatment with HGT-1410 up to 8 years.

Pharmacokinetic Variables:

N/A.

Safety Assessments:

Safety evaluations will include vital signs, physical examinations, AE assessments, electrocardiograms (ECG); serum chemistry, hematology, urine laboratory tests, and screening for antibodies to rhHNS (in CSF and serum).

Statistical Methods: The statistical methodology supporting the trial will focus on descriptive rather than inferential approaches, given the early phase and objectives of the trial. Data will be plotted and the mean, standard deviation, median, minimum, and maximum for each variable will be tabulated by dose group to look for gross trends over time, which may be attributed to treatment. For continuous data, 95% confidence interval (CI) around the mean will also be estimated and presented.

The analysis population consists of all eligible patients from HGT-SAN-055 who have completed Study HGT-SAN-055 and agreed to participate in this extension study. Safety analyses will be performed using the above mentioned population. The data will be presented by dose group.

Date of Original Protocol: 21 June 2010

Date of Amendment 7: 08 February 2016

LIST OF ABBREVIATIONS AND DEFINITIONS OF TERMS

Abbreviation	Definition
ABR	auditory brainstem response
AE	adverse event
ALB	albumin
ALK-P	alkaline phosphatase
ALT	alanine aminotransferase (SGPT)
AST	aspartate aminotransferase (SGOT)
βhCG	human chorionic gonadotropin
BSID-III	Bayley Scales of Infant Development, Third Edition
BBB	blood brain barrier
BUN	blood urea nitrogen
Ca	calcium
CE	Conformité Européenne
CFR	Code of Federal Regulations
CHQ-50	Child Health Questionnaire™ Parent Form 50
CHQ-87	Child Health Questionnaire™ Child Form 87
CK	creatine kinase
Cl	chloride
CNS	central nervous system
CO ₂	carbon dioxide
CTCAE	Common Terminology Criteria for Adverse Events
CRO	contract research organization
CRIM	cross-reacting immunologic material
CS	clinically significant
CSF	cerebrospinal fluid
ECG	electrocardiogram
eCRF	electronic case report form
EDC	Electronic Data Capture

Abbreviation	Definition
ERT	enzyme replacement therapy
EOS	end of study
EOW	every other week
EU	European Union
FDA	Food and Drug Administration
FPSS/TDS	Four-Point Scoring System/Total Disability Score
GAG	glycosaminoglycan
GCP	Good Clinical Practice
GGT	gamma glutamyl transferase
Hct	hematocrit
Hgb	hemoglobin
HS	heparan sulfate
ICH	International Conference on Harmonization
IDDD	intrathecal drug delivery device
IEC	Independent Ethics Committee
IFU	instructions for use
IND	Investigational New Drug
IRB	Institutional Review Board
IT	intrathecal
ITQOL	Infant Toddler Quality of Life Questionnaire™
IV	intravenous
K	potassium
KABC-II	Kaufman Assessment Battery for Children, Second Edition
LDH	lactic dehydrogenase
LP	lumbar puncture
LSD	lysosomal storage disease
M6P	mannose-6-phosphate
MABC-2	Movement Assessment Battery for Children, Second Edition

Abbreviation	Definition
MCH	mean corpuscular hemoglobin
MCHC	mean corpuscular hemoglobin concentration
MCV	mean corpuscular volume
MedDRA	Medical Dictionary for Regulatory Activities
MPS	Mucopolysaccharidosis
MPS IIIA	Mucopolysaccharidosis IIIA or Sanfilippo syndrome Type A
MRI	magnetic resonance imaging
Na	sodium
NCI	National Cancer Institute
NCS	not clinically significant
PE	pressure-equalization
QoL	quality of life
Q4W	once per month
RBC	red blood cell (count)
rhHNS	recombinant human heparan N-sulfatase
RNA	ribonucleic acid
SAE	serious adverse event
SAP	Statistical Analysis Plan
SBRS	The Sanfilippo Behavior Rating Scale
SGOT	serum glutamic oxaloacetic transaminase (AST)
SGPT	serum glutamic pyruvic transaminase (ALT)
Shire HGT	Shire Human Genetic Therapies, Inc.
TMF	Trial Master File
TX	treatment
UADE	unanticipated adverse device effect
US	United States
VABS-II	Vineland Adaptive Behavior Scales
WBC	white blood cell (count)
WHO-DD	World Health Organization-Drug Dictionary

